4.2.2 Handling of missing data for AE

For analyses of AEs, a complete date must be established to correctly identify the AE as occurring during treatment or not. For purposes of imputing missing components of partially reported start and stop dates for AEs, the algorithms listed below will be followed. In the event of ambiguity or incomplete data which makes it impossible to determine whether the AE was treatment emergent, the AE will be considered treatment emergent. If an imputed date occurs after a study participant's date of death, the imputed date will be set to the date of death.

Although the algorithms for treatment-emergence depend on the onset date, imputation rules are provided for stop date as well, as these may be needed for certain statistical analyses, such as an analyses of AE prevalence or AE duration.

Start and stop dates of AEs will be displayed as reported in the study participant data listings (ie, no imputed values will be displayed in data listings).

Imputation of Partial Start Dates

- If only the month and year are specified and the month and year of first dose is not the same as the month and year of AE onset, then use the 1st of the month

- If only the month and year are specified and the month and year of first dose is the same as the month and year of AE onset, then use the date/time of first dose
- If only the month and year are specified, and the study participant did switch treatment during that month and year, then use the date of first switch treatment.
- If only the year is specified, and the year of first dose is not the same as the year of AE onset, and if the study participants did not switch from placebo to bimekizumab at Week 16, then use January 1 of the year of AE onset
- If only the year is specified, and the year of first dose is the same as the year of AE onset, then use the date/time of first dose
- If only the year is specified, and the year of first dose is the same as the year the study participant did switch treatment, then use the date of first switch treatment.
- If only the year is specified, and the year of first dose is the same as the year of the AE onset and the same as the year the study participant did switch treatment, then use the date of first dose.
- If the imputed stop date is prior to the imputed start date
 - For missing start day and start month:

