 - If the year of start date is the same as the year of first dose and the imputed stop date is on or after the date of first dose then set the start date to the date of first dose
 - Otherwise set to the 1st January of the year of the start date
 - For missing start day only
 - If the month and year of the start date is the same as the month and year of first dose and the imputed stop date is on or after the date of first dose then set the start date to the date of first dose
 - If the month and year of the start date is the same as the month and year of first dose and the imputed stop date is before the date of first dose then set the start date to the 1st of that month
- If the AE onset date is completely unknown, then use the date of first dose

Imputation of Partial Stop Dates:

- If only the month and year are specified, then use the last day of the month
- If only the year is specified, then use December 31st of that year
- If the AE is resolved and the stop date is completely unknown, then do not impute the stop date

Other imputation

In addition, the following will apply for presenting AE in summary tables:

- If the intensity of an AE is unknown, it will be considered as severe.
- If the relationship to study drug is missing, it will be considered as related.

For seriousness, no imputation rule will be applied for the interim analyses, but the worst-case approach will be applied for the final analysis (ie, the missing seriousness will be considered as serious if missing).

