4.2.3 Handling of missing data for prior and concomitant medications

Any medications with incomplete start and end dates/times will be handled according to the following rules for classification as prior and concomitant and for the calculation of relative study days. In the event of ambiguity or incomplete data which makes it impossible to determine whether a medication was concomitant or not, the medication will be considered as concomitant. Such imputations will only be performed for these classifications and calculations; in the listings all data will be shown as recorded on the electronic case report form (eCRF).

Imputation of Partial Start Dates

- If only the month and year are specified and the month and year of first dose is not the same as the month and year of the start date, and the study participant did not switch treatment during that month and year, then use the 1st of the month
- If only the month and year are specified and the month and year of first dose is the same as the month and year of the start, then use the date of first dose
 - If this is leading to a start date after the stop date of then use the 1st of the month
- If only the month and year are specified, and the study participant did switch treatment during that month and year, then use the date of first switch treatment.
- If only the year is specified, and the year of first dose is not the same as the year of the start date and the study participant did not switch treatment during that year, then use January 1 of the year of the start date
- If only the year is specified, and the year of first dose is the same as the year of the start date, then use the date of first dose
- If the start date is completely unknown, and the stop date is unknown or not prior to the date of first dose, then use the date of first dose
- If the imputed stop date is prior to the imputed start date
 - If the year of start date is the same as the year of first dose and the stop date is after the date of first dose then set the start date to the date of first dose
 - Otherwise set to the 1st January of the year of the start date

Imputation of Partial Stop Dates

- If only the month and year are specified, then use the last day of the month
- If only the year is specified, then use December 31 of that year
- If the stop date is completely unknown, do not impute the stop date

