10.2 Adverse events

Adverse events with start date prior to first administration of study medication are defined as pre-treatment AEs. No summaries of these events will typically be produced although they will be included in listings.

Adverse events that started more than 140 days after the last administration of study medication are defined as post-treatment AEs. Such events will not be included in any tabulated summaries but will be listed.

Treatment-emergent AEs (TEAEs) are defined as those AEs that have a start date on or following the first dose of study treatment through the final dose of study treatment + 140 days (covering the 20-week SFU period).

All summaries will be provided by treatment group. The treatment group for each study participant will be defined as the treatment received at the onset of the AE. If the onset of the AE occurs on the day where the study participant switches treatment from the Double-Blind Treatment Period to the Maintenance Period and receives a new treatment, it will be attributed to the originally randomized study treatment. The only exception to this is if the AE fulfills the criteria for an anaphylactic reaction. See Section 3.7 for further details.

AEs will be presented as “number of study participants (percentage of study participants) [number of events]”. In this style of output, “[number of events]” will include all cases of an AE including repeat occurrences in individual study participants, while “number of study participants” will count each study participant only once.

Adverse event summaries by SOC, HLT and PT will be ordered alphabetically for SOC and HLT within SOC and in terms of decreasing frequency for PT within HLT in the bimekizumab treatment group and then similarly by decreasing frequency in the placebo group.

AE summaries by PT will be ordered in terms of decreasing frequency for PT within the bimekizumab treatment group, and in the event of ties, PT will be sorted alphabetically.

Study participant time at risk represents the time a study participant is at risk for having an AE. The definitions for study participant time at risk (in days) are outlined in Section 10.1. These definitions will be used for exposure-adjusted AE summaries.

Selected AE summaries will include the exposure adjusted incidence rate (EAIR) with associated 95% confidence interval and the exposure adjusted event rate (EAER).

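### An adverse event with unknown onset is dated to the first dose even when its stop date is earlier, so it counts as treatment-emergent; separately, two start-date rules conflict for the switch month

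*SAP*

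**What the plan says.** Section 4.2.2 sets start-date rules by how much of the onset date is reported.

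- **Nothing reported:** "If the AE onset date is completely unknown, then use the date of first dose". No condition is attached.
- **Month and year reported, month differs from that of first dose:** the month of first dose "is not the same as the month and year of AE onset, then use the 1st of the month".
- **Month and year reported, switch in that month:** if "the study participant did switch treatment during that month and year, then use the date of first switch treatment".

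A repair block is triggered by "If the imputed stop date is prior to the imputed start date". It has two branches. The branch for a missing day and month ends with "Otherwise set to the 1st January of the year of the start date". The branch for a missing day only has two sub-rules, and both open with "If the month and year of the start date is the same as the month and year of first dose".

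Section 10.2 classifies by start date alone: "Adverse events with start date prior to first administration of study medication are defined as pre-treatment AEs". Events starting from first dose up to 140 days after the final dose are treatment-emergent.

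Section 4.2.3, on medications, uses the first-dose date for a wholly unknown start only when the start is unknown "and the stop date is unknown or not prior to the date of first dose, then use the date of first dose". Its 1st-of-month rule also excludes months in which the participant switched treatment.

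**The concern.** Section 4.2.2 treats an event as treatment-emergent by default only where the data leave the question undecidable. A stop date before first dose decides it. The same holds when the stop date is partial, because Section 4.2.2 completes it to the last day of the month or year. If even that latest possible stop precedes first dose, the event was over before treatment.

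The unknown-onset rule nevertheless places such an event on the first-dose day. It then enters the treatment-emergent tables, including the placebo-controlled ones for the Double-Blind Treatment Period. In the exposure-adjusted incidence rate of Section 10.2, exposure runs from first dose to first occurrence, so the event adds a case with essentially no exposure time. The derived record also has an onset later than its stop.

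In the switch month, two programmers following the text could derive different onset dates for the same event. One of those dates can fall after the event ended.

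**Working it through.** The SAP states no figure here, so the check is one of date logic. The start-date rules and the repair block were applied to assumed dates: first dose 20 Mar 2020, and switch 112 days (16 weeks) later, on 10 Jul 2020. The check assumes that the repair block may act on a reported stop date. Its wording mentions only an imputed one.

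| Onset reported | Stop | Start from the rule | Repair branch | Result |
|---|---|---|---|---|
| (a) nothing | 10 Mar 2020 | 20 Mar 2020 | none applies | start 10 days after stop; treatment-emergent |
| (b1) Jul 2020, 1st-of-month rule | 8 Jul 2020 | 1 Jul 2020 | not needed | consistent |
| (b2) Jul 2020, switch rule | 8 Jul 2020 | 10 Jul 2020 | none applies | start 2 days after stop, on the switch day |
| (c) Mar 2020 | 15 Mar 2020 | 20 Mar 2020 | reset to 1 Mar 2020 | pre-treatment |
| (d) 2020 only | 10 Mar 2020 | 20 Mar 2020 | reset to 1 Jan 2020 | pre-treatment |

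A second set (first dose 20 Nov 2020, switch 12 Mar 2021) gave the same pattern. An unknown onset with a stop on 10 Nov was dated 20 Nov. A switch-month event that stopped on 10 Mar 2021 was dated either 1 Mar or 12 Mar.

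**Unknown onset.** In (a), the branch for a missing day and month needs a start year, and the branch for a missing day needs a month and year. Neither exists. In (c) and (d), the same section lets a stop before first dose make the event pre-treatment. Case (a) carries the same decisive information and gets the opposite classification.

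**Switch month.** In (b), both month-level rules are satisfied, because the switch falls about 16 weeks after first dose and so in a different month. Section 4.2.2 does not say which governs. Under (b2) the repair block does not help, because both day-only sub-rules are confined to the month of first dose.

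**Attribution under (b2).** Sections 3.7 and 10.2 assign a switch-day event to placebo. Section 3.7 excepts anaphylactic and hypersensitivity reactions and the administration-site and injection-site terms, which go to bimekizumab. The Maintenance Period for safety data starts on that day (Section 3.2.2.1.1), but that section refers to Section 3.7 for events on dosing days.

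**The case against.** The best defence of the unknown-onset rule is that the first repair branch could be read to cover it. Its heading, missing day and month, is literally true of a wholly unknown onset, and the year could be taken from the imputed start. A stop before first dose would then lead to 1 January and pre-treatment status. This reading is strained. The branch relies on the year of the start date, and the unknown-onset rule follows the block as a separate item. Even on this reading, onset could still follow a stop from an earlier calendar year.

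The intent is also visible elsewhere. Section 3.2.1.1 speaks of non-treatment-emergent events that started and stopped before first dose, and the default in Section 4.2.2 is limited to undecidable cases. That supports the view that this is an omission, but the operative definition in Section 10.2 still uses the start date alone.

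Two mitigating points stand. Screening events precede treatment, so misclassification of this kind is not expected to differ between randomised arms. Listings show dates as reported, so the true stop date remains visible.

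For the switch month, a reader might infer that events which ended on placebo generally become post-switch or bimekizumab events, or that every such event is misdated. The SAP does not support either. The 1st-of-month rule applies equally and gives a sound date, and under the switch rule most events stay with placebo. The demonstrable defect is the missing precedence, with an unrepaired case if the switch rule wins.

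**Conclusion.** The unknown-onset point holds on the natural reading of Section 4.2.2. An event whose stop date precedes first dose is dated after its own end and counted as treatment-emergent although its timing is known. The switch-month point holds in narrower form: two conflicting start dates, no precedence, and no repair if the switch date is chosen. A change of arm then needs all of the following together: a participant switching from placebo, a month-only onset in the switch month, a stop earlier in that month, an event type excepted in Section 3.7, and the switch rule prevailing.

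No count of affected events can be derived from the SAP. It is probably small and may be zero. This is a minor correction, most visible for rare safety topics, where one misplaced event shows in a table. The dates in the check are assumptions that only illustrate the logic.

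**What to change.** 1. In Section 4.2.2, use the first-dose date for a completely unknown onset only if the stop date is unknown or not before first dose. Otherwise classify the event as pre-treatment. The classification must be stated, because the Section 4.2.3 condition only withholds the first-dose date.
2. Exclude switch months from the 1st-of-month rule, as Section 4.2.3 does, so that the switch-date rule governs. Add a repair branch that sets the start to the 1st of that month when the stop date precedes the switch.
3. Let the repair block act on reported as well as imputed stop dates.

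With these changes, case (a) becomes pre-treatment and case (b) starts on 1 Jul 2020 (1 Mar 2021 in the second set), before both its stop and the switch. Cases (c) and (d) are unchanged. The cost is a few sentences in the SAP and a small change to the date-imputation program.

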4.2.3 Handling of missing data for prior and concomitant medications

Any medications with incomplete start and end dates/times will be handled according to the following rules for classification as prior and concomitant and for the calculation of relative study days. In the event of ambiguity or incomplete data which makes it impossible to determine whether a medication was concomitant or not, the medication will be considered as concomitant. Such imputations will only be performed for these classifications and calculations; in the listings all data will be shown as recorded on the electronic case report form (eCRF).

Imputation of Partial Start Dates

- If only the month and year are specified and the month and year of first dose is not the same as the month and year of the start date, and the study participant did not switch treatment during that month and year, then use the 1st of the month
- If only the month and year are specified and the month and year of first dose is the same as the month and year of the start, then use the date of first dose
 - If this is leading to a start date after the stop date of then use the 1st of the month
- If only the month and year are specified, and the study participant did switch treatment during that month and year, then use the date of first switch treatment.
- If only the year is specified, and the year of first dose is not the same as the year of the start date and the study participant did not switch treatment during that year, then use January 1 of the year of the start date
- If only the year is specified, and the year of first dose is the same as the year of the start date, then use the date of first dose
- If the start date is completely unknown, and the stop date is unknown or not prior to the date of first dose, then use the date of first dose
- If the imputed stop date is prior to the imputed start date
 - If the year of start date is the same as the year of first dose and the stop date is after the date of first dose then set the start date to the date of first dose
 - Otherwise set to the 1st January of the year of the start date

Imputation of Partial Stop Dates

- If only the month and year are specified, then use the last day of the month
- If only the year is specified, then use December 31 of that year
- If the stop date is completely unknown, do not impute the stop date

4.3 Interim analysis and data monitoring

4.3.1 Interim analyses

Two interim analyses will be conducted:

- The first interim analysis will be conducted after the planned number of randomized study participants have completed the Double-Blind Treatment Period and the 24 week assessments or have withdrawn from IMP or the study. The purpose of this analysis is to prepare a regulatory submission for a Marketing Authorization Application based on this analysis.
- The second interim analysis will be conducted after the planned number of study participants have completed Week 52 or have withdrawn from IMP or the study. The purpose of this second interim analysis is to perform a comprehensive evaluation of all available data for the study and to supplement the regulatory submission based on the Week 24 interim analysis.

The database for the Week 24 interim analysis will include all available data collected up to the day the last planned study participant completed the Week 24 Visit (even if this study participant has withdrawn from IMP). Study participants who discontinued the study prior to Week 24 will be included in this first interim analysis.

The Week 24 interim analysis will evaluate the primary, secondary and other efficacy variables, as well as the safety and PK/immunogenicity variable results. The disposition, demographics and other Baseline characteristics, protocol deviations and compliance will also be described.

The efficacy analyses will present data until Week 24, and the safety analyses will include all available data collected up to the day the last planned study participant completed the Week 24 Visit. This may include safety data beyond the Week 24 timepoint. Events on-going at the time of the interim analysis (eg, concomitant medications, or adverse events) will be analyzed as they are collected to date (ie, up to Week 24 of last participant for safety endpoints), and analyses based on these events will be revised at time of the second interim analysis and/or final analysis.

For this first interim analysis, a database freeze will be performed, and the treatment codes will be made available to the UCB personnel. An interim CSR report will be written to include efficacy, safety, PK, and ADAb analyses. NAb analyses are not planned for inclusion in the interim CSR report. The investigators and study participants will remain blinded to the assigned bimekizumab dosing regimen until the last study participant completes the study. A blinding maintenance plan will be written to evaluate the potential bias of the Maintenance Period and describe the process of interim results generation and dissemination. The plan will be finalized prior to the freeze of the database at the Week 24 interim analysis.

The Week 52 interim analysis will be conducted similarly as the first interim analysis: the database will include all available data collected up to the day the last study participant completed the Week 52 Visit (even if this study participant has withdrawn from IMP). Study participants who discontinued the study prior to Week 52 will be included in this second interim analysis. The efficacy analyses will present data until Week 52, and the safety analyses will include all available data collected up to the day the last study participant completed the Week 52 Visit.

No formal alterations to the further study conduct (eg, stopping rules, sample size re-estimation, or changes to eligibility criteria) are planned for the two interim analyses.

No separate SAP for the interim analyses will be provided. The TFL shells for the interim and final analyses will be provided in the same document.

The type of efficacy and safety analyses to be provided for the two interim analyses is detailed in [Table 4-3](#).

Table 4–3: Summary of efficacy and safety analyses for each interim analysis

Variable	Analysis Sets (study period)	Treatment groups	Interim Analysis 1	Interim Analysis 2
Type of tables				
Tables on primary efficacy variable	RS, FAS, PPS	
 • Placebo • BKZ 160mg Q4W 	Yes	Yes, rerun of tables provided for interim analysis 1
Tables on secondary efficacy variables	RS	
 • Placebo • BKZ 160mg Q4W 	Yes	Yes, rerun of tables provided for interim analysis 1
Other efficacy variables				
Tables/graph on time to ASAS response	RS (DB-period only)	
 • Placebo • BKZ 160mg Q4W 	Yes, for all visits up to Week 16 for each participant	Yes, rerun of analyses provided for interim analysis 1
By-visit tables	RS	
 • Placebo • BKZ 160mg Q4W 	Yes, for all visits up to Week 24 for each participant	Yes, for all visits up to Week 52 for each participant
Safety Variables				
Tables of adverse events	SS (DB-period only)	
 • Placebo • BKZ 160mg Q4W 	Yes, for all visits up to Week 16 for each participant	No
	MS (MP only)	
 • BKZ 160mg Q4W Total 	No	Yes, from Week 16 up to Week 52 for each participant
	SS (Overall period)	
 • BKZ 160mg Q4W Total 	Yes, for all visits up to date of Week 24 visit of last planned participant	Yes, for all visits up to date of Week 52 visit of last planned participant
By-visit tables on laboratory or VS data	SS (Overall period)	
 • Placebo / BKZ 160mg Q4W • BKZ 160mg Q4W 	Yes, for all visits up to date of Week 24 visit of last planned participant	Yes, for all visits up to date of Week 52 visit of last planned participant

Variable	Analysis Sets (study period)	Treatment groups	Interim Analysis 1	Interim Analysis 2
Type of tables Shift table or table on TEMA for laboratory data or Hy's Law cases	SS (DB-period only)	
 Placebo BKZ 160mg Q4W 	Yes, for all visits up to Week 16 for each participant	No
	MS ^a (MP only)	
 BKZ 160mg Q4W Total 	No	Yes, from Week 16 up to Week 52
	SS ^a (Overall period)	
 BKZ 160mg Q4W Total 	Yes, for all visits up to date of Week 24 visit of last planned participant	Yes, for all visits up to date of Week 52 visit of last planned participant
Table on TEMA for VS data	SS (DB-period only)	
 Placebo BKZ 160mg Q4W 	Yes, for all visits up to Week 16 for each participant	No
	MS ^a (MP only)	
 BKZ 160mg Q4W Total 	No	Yes, from Week 16 up to Week 52 for each participant
	SS ^a (Overall period)	
 BKZ 160mg Q4W Total 	Yes, for all visits up to date of Week 24 visit of last planned participant	Yes, for all visits up to date of Week 52 visit of last planned participant
Tables on ECG or tuberculosis data	SS (Overall period)	
 Placebo / BKZ 160mg Q4W BKZ 160mg Q4W 	Yes, for all visits up to date of Week 24 visit of last planned participant	Yes, for all visits up to date of Week 52 visit of last planned participant
Tables on PHQ-9 data	SS (Overall period)	
 Placebo / BKZ 160mg Q4W BKZ 160mg Q4W 	Yes, for all visits up to date of Week 24 visit of last planned participant	Yes, for all visits up to date of Week 52 visit of last planned participant
Tables on eC-SSRS data	SS (DB-period only)	
 Placebo BKZ 160mg Q4W 	Yes, for all visits up to Week 16 for each participant	No

This document cannot be used to support and marketing authorization application or variations thereof.

Variable	Analysis Sets (study period)	Treatment groups	Interim Analysis 1	Interim Analysis 2
Type of tables	MS (MP only)	
 • BKZ 160mg Q4W Total 	No	Yes, from Week 16 up to Week 52 for each participant
	SS (Overall period)	
 • BKZ 160mg Q4W Total 	Yes, for all visits up to date of Week 24 visit of last planned participant	Yes, for all visits up to date of Week 52 visit of last planned participant

^a For placebo-randomized study participants, results are determined based on the Baseline Week 16 (See Section 3.3).

Study participants in the Placebo/ BKZ 160mg Q4W treatment group are taking BKZ 160 mg Q4W treatment after Week 16.

The final analysis will occur once last study participant has completed the SFU Visit. The final analysis will consist of a rerun of all listings and all safety summary analyses created for the Week 52 interim analysis but will include data occurring during the SFU period that were not available for the Week 52 interim analysis.

